#### 8.5.4. Reporting of serious adverse events and other events

SAEs that occur in the time period defined in Section 8.5.2 will be reported promptly to GSK within the timeframes described in Table 15, once the investigator determines that the event meets the protocol definition of an SAE.

pIMDs that occur in the time period defined in Section 8.5.2 will be reported promptly to GSK within the timeframes described in Table 15, once the investigator determines that the event meets the protocol definition of a pIMD.

**Table 15 Timeframes for submitting serious adverse event, and other events reports to GSK**

Type of Event	Initial Reports		Follow-up of Relevant Information on a Previous Report	
	Timeframe	Documents	Timeframe	Documents
SAEs	24 hours*‡	electronic Expedited Adverse Events Report	24 hours*	electronic Expedited Adverse Events Report
pIMDs	24 hours**‡	electronic Expedited Adverse Events Report	24 hours*	electronic Expedited Adverse Events Report

\* Timeframe allowed after receipt or awareness of the information.

\*\*Timeframe allowed once the investigator determines that the event meets the protocol definition of a pIMD.

‡ The investigator will be required to confirm review of the SAE causality by ticking the 'reviewed' box in the electronic Expedited Adverse Events Report within 72 hours of submission of the SAE or pIMD.

#### **8.5.4.2. Regulatory reporting requirements for SAEs**

Prompt notification of an SAE by the investigator to the sponsor is essential for meeting legal obligations and ethical responsibilities for the safety of subjects and the safety of a study treatment under clinical investigation.

The sponsor has a legal responsibility to notify both the local regulatory authority and other regulatory agencies about the safety of a study treatment under clinical investigation. The sponsor will comply with country-specific regulatory requirements relating to safety reporting to the regulatory authority, Institutional Review Boards (IRB)/Independent Ethics Committees (IEC), and investigators.

Investigator safety reports must be prepared for suspected unexpected serious adverse reactions (SUSAR) according to local regulatory requirements and sponsor policy and forwarded to investigators as necessary.

An investigator who receives an investigator safety report describing an SAE or other specific safety information (e.g. summary or listing of SAE) from the sponsor will review and then file it along with the Investigator's Brochure and will notify the IRB/IEC, if appropriate according to local requirements.

#### **8.5.5. Follow-up of AEs and SAEs**

After the initial report of AE, SAE or pIMD (serious or non-serious), the investigator is required to proactively follow each subject at subsequent visits/contacts. All SAEs or pIMDs (serious or non-serious), will be followed until the event is resolved, stabilized, otherwise explained, or the subject is lost to follow-up. Further information on follow-up procedures is given in Section [12.5.10](#).

#### **8.5.6. Treatment of adverse events**

Treatment of any AE is at the sole discretion of the investigator and according to current good medical practice. Any medication administered for the treatment of an SAE or pIMD should be recorded in Expedited Adverse Event Report of the subject's eCRF (refer to Section [7.5](#)).

#### **8.5.7. Clinical safety laboratory assessments**

Refer to Section [12.2](#) (Appendix 2) for the list of clinical laboratory tests to be performed and to the SoA (Section [2](#)) for the timing and frequency.

- The investigator must review the laboratory report, document this review, and record any clinically relevant changes occurring during the study in the AE section of the eCRF. The laboratory reports must be filed with the source documents. Clinically significant abnormal laboratory findings are those which are not associated with an underlying disease, unless judged by the investigator to be more severe than expected for the subject's condition.

- All laboratory tests with values considered clinically significant abnormal during participation in the study or within 7 days after the last dose of study treatment should be repeated until the values return to normal or baseline or are no longer considered significantly abnormal by the investigator or medical monitor. Refer to the Section 12.5.6 for clinical laboratory abnormal assessments qualified as AEs or SAEs.
- If such values do not return to normal/baseline within a period of time judged reasonable by the investigator, the etiology should be identified and the sponsor notified.

All protocol-required laboratory safety assessments, as defined in Section 12.2 (Appendix 2), must be conducted in accordance with the laboratory manual and the SoA (Section 2).

#### **8.5.8. Subject card**

Study subjects must be provided with the address and telephone number of the main contact for information about the clinical study.

The investigator (or delegator) must therefore provide a “subject card” to each subject. In an emergency situation, this card serves to inform the responsible attending physician that the subject is in a clinical study and that relevant information may be obtained by contacting the investigator.

Subjects must be instructed to keep subject cards in their possession at all times during the study duration.

#### **8.5.9. Safety follow-up calls**

At the Month 8 and Month 14 telephone contacts, subjects will be queried in accordance with a template script provided separately by GSK. The subjects will be queried about concomitant medications and the occurrence of pIMDs, SAEs, concurrent vaccination, SAEs related to study participation or to a concurrent GSK medication/vaccine, and AEs or SAEs leading to withdrawal. Information collected will be documented in the source document and will be recorded in the eCRF.

## 8.6. RTI Surveillance

RTI surveillance comprises active and passive surveillance. Both active and passive surveillance will only be carried out during the RSV seasons (from August until end of February), as based on local data. According to a surveillance study assessing the seasonality in 19 different countries, the RSV season from 2010 to 2017 in Japan specifically was found to start between late July and early November and continue through February with a peak seen between early October to early December. Information regarding the regional variability was not available [[Obando-Pacheco](#), 2018]. These findings are similar to that reported by the Infectious Agents Surveillance Report (IASR) in their weekly report detecting RSV from 2007 onward in Japan [[IASR](#), 2014] with a seasonality which approximates that of North America [[Saijo](#), 1994]. In most recent seasons, RSV epidemics have been observed as beginning earlier, accompanied with a rapid increase in the number of reports since early July, 2018 [[IDWR](#), 2018].

### 8.6.1. Active surveillance

During the RSV seasons, study participants will be contacted by the investigator/study staff every 2 weeks to identify if they experience RTI symptoms (i.e., cough, runny nose, fever [ $\geq 37.5^{\circ}\text{C}$ ] or difficulty to breathe). A template script will be provided separately by GSK.

In case of RTI symptoms (at least 3; see Section [8.6.3](#)) reported by the subject, the subject will be asked to collect a nasal swab at home ideally within 48 hours after the start of symptoms. An assessment visit for nasal and throat swab specimen collection by qualified staff from the study team will be scheduled. The assessment visit should take place as soon as possible after the start of symptoms (ideally within 48 hours, but no later than 7 days). Episodes should be treated accordingly to local standard of care.

In the event that it is not possible to schedule an assessment visit, the assessment visit page of the eCRF should be filled in as completely as possible using available medical records.

### 8.6.2. Passive surveillance

Study participants will be instructed to contact the investigator/study staff in case of RTI symptoms during the RSV seasons (e.g., cough, runny nose, fever [ $\geq 37.5^{\circ}\text{C}$ ] or difficulty to breathe).

In case of RTI symptoms (at least 3) reported by the subject, the subject will be asked to collect a nasal swab at home within 48 hours after the start of symptoms and contact the investigator/study staff, who will schedule an assessment visit for nasal and throat swab specimen collection by qualified staff from the study team. The assessment visit should take place as soon as possible after the start of symptoms (ideally within 48 hours, but no later than 7 days). Episodes should be treated according to local standard of care.

In the event that it is not possible to schedule an assessment visit, the assessment visit page of the eCRF should be filled in as completely as possible using available medical records.

### **8.6.3. Assessment Visit for potential RSV-RTI**

The purpose of the Assessment Visit for potential RSV-RTI is to objectively document signs and symptoms (e.g., cough, runny nose, fever [ $\geq 37.5^{\circ}\text{C}$ ] or difficulty to breathe) by an appropriately qualified person (i.e., medical or nursing) and to take nasal and throat swabs for detection of RSV infection. The visit should take place as soon as possible after the start of symptoms (ideally within 48 hours, but no later than 7 days).

- Assessment visits may take place in the study participant's home, the investigator's clinical facility or a medical facility as appropriate to the circumstances in the judgment of the investigator.
- If the reported symptoms are already of a level of severity that urgent care is indicated, the study participant should be redirected to the proper location to receive this care (e.g. Emergency Room) and an assessment visit could be scheduled to take place there at a suitable time.
- For self-collection as well as staff-collection, swabs for analysis at sponsor laboratory should be collected when subjects show at least 3 of the following signs/symptoms:
  - Nasal congestion,
  - Sore throat,
  - Earache,
  - New or worsening cough,
  - New or worsening sputum,
  - Dyspnea,
  - Rhinorrhea,
  - Wheezing (whistling, musical or puffing sound made on exhalation) or worsening of wheezing,
  - Rales (crackles),
  - Rhonchi (sound with musical pitch during inspiration or expiration),
  - Fever (temperature of  $\geq 37.5^{\circ}\text{C}$ ) or feeling feverish.

- During the assessment visit, the investigator/study staff will evaluate the clinical signs and symptoms of the RTI and measure the subject's resting vital signs (systolic/diastolic blood pressure, pulse oximetry, heart rate, respiratory rate after at least 10 minutes of rest) and temperature. RTI symptoms include, but may not be limited to, the following:
  - **Upper respiratory symptoms:** nasal congestion, sore throat, rhinorrhea, earache.
  - **Lower respiratory symptoms:** new or worsening cough, new or worsening of sputum production, dyspnea, wheezing or worsening of wheezing, rales (crackles), rhonchi.
  - **Systemic symptoms:** myalgia, arthralgia, fatigue, headache, decreased appetite, feverishness, pain (localized at chest or abdomen at respiration).
- Signs and symptoms, resting vital signs, temperature and onset date of first symptom should be recorded within the RTI episode screen in the eCRF.
- Following the assessment visit, study participants will be instructed to contact the study staff if the severity of the already existing symptoms increases or if they develop difficulty in breathing or wheezing, and this may lead to a repeat assessment visit upon the judgment of the investigator.
- The status and evolution of the case will be followed until case resolution, as per routine practice.
- RTI data will be entered in the eCRF:
  - A new episode number and section will be created in the eCRF for each RTI episode.
  - All data pertaining to a same episode (including date of onset and end date) will be entered under the same eCRF episode number, even if observations are consolidated from several visits or contacts.

## 8.7. Holding rules and safety monitoring

An iSRC will be appointed and operating under a charter, in addition to the existing project's Safety Review Team. Safety holding rules have been defined ([Table 17](#), [Table 18](#)). The iSRC will review the protocol and Statistical Analysis Plan (SAP). Meetings will be documented and in case open sessions are held at the iSRC meetings, the minutes from these open sessions will be made available to the study team. The iSRC may, if deemed necessary, convene a meeting with, or request further information from GSK's designated project representatives at any stage of the study.

The iSRC will conduct unblinded reviews of all available safety data (as clean as possible) from the present study, while taking into account any other findings that could have an impact on the safety of the subjects, and will determine whether there is a safety signal that needs to be escalated to the sponsor.

Other GSK studies evaluating the same antigen in the RSV older adults or RSV maternal program may be running at a time that can overlap with the conduct of this study. Any relevant safety information from these other GSK studies with the same antigen will be shared with the iSRC of the Japan study; the holding rules of these other studies might also impact the Japan study, and vice versa.

### **Overview of safety monitoring:**

- All participants will be closely observed for a minimum of 60 minutes after each vaccination.
- All available data from the participants vaccinated with the first dose will be reviewed in a first iSRC meeting. This iSRC will perform a safety evaluation of all available data collected up to 7 days post-Dose 1. Holding rules described in [Table 18](#) will apply.
- If the outcome of the first iSRC evaluation is favorable, participants will receive the second dose.
- A second iSRC meeting will review all available safety data up to 30 days post-Dose 2.
- During the follow-up phase, 2 iSRC meetings will be planned with an interval of approximately 6 months. For the last of these iSRC evaluations, the end-of-study Clinical Study Report will be provided to the iSRC for review.
- If any safety concern is identified by the investigator (i.e., meeting of holding rules 1a-1c [see [Table 17](#)] or any other safety concern), he/she should hold vaccination and inform GSK immediately (within 24 hours). GSK will confirm the hold of the vaccination and call for an ad-hoc iSRC if needed.

#### **8.7.1. Outcome of safety evaluation**

- If **no safety signal** is observed, the favorable outcome of the safety evaluations will be documented and provided in writing, authorizing the investigator to start vaccination of subjects with the subsequent dose.
- If a **safety signal** is observed during the safety evaluations or if any of the holding rules 2a-d is met, the iSRC Chair (or his/her representative) is responsible for the urgent communication to GSK, including the rationale for the decision to put the vaccination on hold or not.
- The study Clinical Research and Development Lead (CRDL) will be accountable for notifying all investigators of the decision whether to suspend, modify or continue the conduct of the study.

Refer to Section [8.7.2](#) for an overview of the communication flow in case a holding rule is met, as identified by the Investigator or iSRC.

### 8.7.1.1. Process of stopping the vaccination

In the event that a safety signal is observed, the sponsor might decide to cancel vaccination.

In this case:

- Subjects who were already vaccinated will not receive the second study vaccine dose (if not yet administered) and continue all other visits as planned.
- Subjects who signed an informed consent but did not receive any study vaccine will be informed that their study participation will be stopped.

### 8.7.2. Study holding rules

The safety holding rules are defined in [Table 17](#) and [Table 18](#).

Holding rules 1a-1c from [Table 17](#) will be assessed by the investigator on a continuous basis and meeting any of these holding rules will trigger a hold of vaccination, irrespective of the number of subjects enrolled and/or timing of the event relative to vaccination. The safety holding rules 2a – 2d from [Table 18](#) will be assessed by iSRC during the first safety evaluation on unblinded data. These holding rules have been written under the assumption that the safety data from all subjects will be available. If the data from all subjects are not available (i.e. in case a subject is lost to follow-up), then the holding rules will be assessed by the iSRC on a pro-rata basis.

Of note, no formal holding rules will be applied for other safety data such as non-life-threatening SAEs that cannot reasonably be attributed to the study vaccination (non-life-threatening non-related SAEs), missed visits due to vaccine-related AEs, Grade 1 and Grade 2 solicited, unsolicited AEs in the 7-day follow-up period, unsolicited AEs collected from Day 8 to Day 30 after vaccination. However, these data, if available, will also be reviewed by the iSRC in order to allow for an overall assessment of the benefit/risk ratio of vaccination.

**Table 17 Study holding rules identifiable by the investigator**

Holding Rule	Event	Number of subjects
1a	Death or any life-threatening SAE	≥ 1
1b	Any non-life-threatening SAE that cannot reasonably be attributed to a cause other than vaccination (non-life-threatening related SAEs)	≥ 1
1c	Any local or general solicited AE leading to hospitalization , or fever > 40°C that cannot reasonably be attributed to a cause other than vaccination, or necrosis at the injection site, within the 7-day (Day 1-7) post-vaccination period	≥ 1

**Table 18      Study holding rules identifiable by the iSRC**

Holding Rule	Event	Percentage (number of subjects/group/dose)
2a	Any withdrawal from the study (by investigator or subject request) following a Grade 3 AE that cannot reasonably be attributed to a cause other than vaccination	≥ 25% (5/20)
2b	Any Grade 3 solicited local AE lasting 48h or more in an investigational RSV vaccine group, within the 7-day (Day 1-7) post-vaccination period	≥ 25% (5/20)
2c	Any Grade 3 solicited general AE lasting 48h or more in an investigational RSV vaccine group, that cannot reasonably be attributed to a cause other than vaccination, within the 7-day (Day 1-7) post-vaccination period	≥ 25% (5/20)
2d	Any ≥ Grade 3 unsolicited AE in an investigational RSV vaccine group, that cannot reasonably be attributed to a cause other than vaccination, within the 7-day (Day 1-7) post-vaccination period OR Any ≥ Grade 3 abnormality in pre-specified hematological or biochemical laboratory parameters in an investigational RSV vaccine group, up to the Day 8 post-vaccination visit. †	≥ 25% (5/20)

† Grading of laboratory parameters will be based on the FDA Guidance for Industry “Toxicity Grading Scale for Healthy Adults and Adolescent Volunteers Enrolled in Preventive Vaccine Clinical Trials” (Refer to Section 12.7, Appendix 7). Those laboratory parameters not included in the FDA Toxicity Grading Scale will not be graded.

The investigator is not permitted to start the administration of the next dose until receipt of the favorable outcome of the safety evaluation, documented and provided in writing, authorizing the investigator to proceed.

Moreover, if the investigator becomes aware of a holding rule being met, he/she will suspend vaccination and will inform GSK immediately (e.g. meeting of holding rules 1a-c).

The below flow of communication has to be followed:

In order to provide an effective study conduct, a proper communication plan will be set up between investigators, Local Operating Company (LOC) personnel, Central functions and the iSRC. This communication plan will allow an effective vaccination halt as well as restart or suspend of vaccination.

### **Holding rules identified by Investigators**

If a holding rule is met at the site level, vaccination must be put on hold immediately in each study center and the study Local Medical Lead (LML) in the LOC should be informed. The LOC will inform the central study team (study CRDL, Study Delivery Lead, and Safety Physician). All other procedures relating to safety and immunology will continue.

Following an internal review as well as review by the iSRC, the Sponsor will decide to continue the conduct of, suspend or modify the study. This decision will be documented and provided in writing to the investigators.

## Holding rules identified by the iSRC

[figure not shown]
If a holding rule is met following safety evaluation by the iSRC, the iSRC Chairman must notify the primary GSK contact immediately. The central study team (study CRDL, Study Delivery Lead, or Safety Physician) will subsequently inform the LOC and Investigators from each study center. All vaccinations will cease immediately, but all other procedures relating to safety and immunology will continue.

Following additional assessment by the iSRC, the Sponsor will decide to continue the conduct of, suspend or modify the study. This decision will be documented and provided in writing to the investigators.

### 8.7.3. Risk assessment

Figure 2 gives the probability of not meeting each holding rule 1 and 2 for 20 subjects per group.

**Figure 2 Evaluations based on 20 subjects per group - risk assessment curve for 1 group based on the proposed safety holding rules**

The above figure illustrates that, with 20 subjects per study group:

- Each holding rule 1a-c has more than 90% chance of not being met for vaccination with a true incidence rate below 1% and has more than 88% chance of being met for vaccination with a true incidence rate above 10%.
- Each holding rule 2a-d has more than 80% chance of not being met for vaccination with a true incidence rate below 16% and more than 60% chance of being met for vaccination with a true incidence rate above 25%.

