## 10. STATISTICAL CONSIDERATIONS

### 10.1. Sample size determination

#### 10.1.1. Sample size calculation

A sample size of 20 subjects per group would provide a probability of 80% or 90% to observe at least one AE, if the true AE rate is 7.8% or 10.9%, respectively.

Considering a sample size of 20 subjects per group, [Table 19](#) below illustrates the exact 95% Confidence Intervals (CIs) for the different possible numbers of AEs within each group.

**Table 19 Two-sided 95% exact confidence intervals based on the percentage of subjects with adverse events following vaccination of 20 subjects per group**

Number (%) of subjects with an AE	Exact 95% Confidence Interval (CI)	
	Lower Limit (%)	Upper limit (%)
0 (0%)	0.00	16.84
1 (5%)	0.13	24.87
2 (10%)	1.23	31.70
3 (15%)	3.21	37.89
4 (20%)	5.73	43.66
5 (25%)	8.66	49.10
6 (30%)	11.89	54.28
7 (35%)	15.39	59.22
8 (40%)	19.12	63.95
9 (45%)	23.06	68.47
10 (50%)	27.20	72.80
11 (55%)	31.53	76.94
12 (60%)	36.05	80.88
13 (65%)	40.78	84.61
14 (70%)	45.72	88.11
15 (75%)	50.90	91.34
16 (80%)	56.34	94.27
17 (90%)	62.11	96.79
18 (95%)	68.30	98.77
19 (95%)	75.13	99.87
20 (100%)	83.16	100.00

Exact 95% CI computed based on Clopper/Pearson formula.

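### Section 8.7.3 overstates the chance that holding rules 1a-c are not met: at 1% incidence in a group of 20 it is 81.8%, not more than 90%

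*Protocol*

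**What the plan says.** Protocol section 8.7.3 describes the operating characteristics of the safety holding rules. It introduces the curve by saying that "Figure 2 gives the probability of not meeting each holding rule 1 and 2 for 20 subjects per group", and its summary begins "The above figure illustrates that, with 20 subjects per study group". For the single-event rules it states: "Each holding rule 1a-c has more than 90% chance of not being met for vaccination with a true incidence rate below 1"%. The same sentence adds that each such rule "has more than 88% chance of being met for vaccination with a true incidence rate above 10"%. For rules 2a-d it gives more than 80% not met below 16%, and "more than 60% chance of being met for vaccination with a true incidence rate above 25"%.

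The rules are in section 8.7.2. Table 17 lists 1a ("Death or any life-threatening SAE"), 1b (a related SAE that is not life-threatening) and 1c (certain severe solicited events within 7 days). In the table's last column the trigger for all three is at least one subject. The text adds that "meeting any of these holding rules will trigger a hold of vaccination, irrespective of the number of subjects enrolled".

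Section 10.1.1 makes a calculation of the same form: "A sample size of 20 subjects per group would provide a probability of 80% or 90% to observe at least one AE", for true rates of 7.8% and 10.9% respectively.

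**The concern.** With a one-subject trigger and 20 subjects, the chance of seeing no event is fixed by the incidence alone, and at 1% it is well under 90%. Section 8.7.3 is where a reader learns how often the rules would pause vaccination when the true risk is low. From the sentence, that reader would expect a given single-event rule to be met in one group less than one time in ten at any incidence up to 1%. If the stated figure is wrong, the chance of a hold at low incidence is understated. Conduct, analysis and subject protection are not at stake.

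**Working it through.** **Inputs.** n = 20 per group, each rule taken separately (section 8.7.3). Trigger for rules 1a-c: at least 1 subject (Table 17). Trigger for rules 2a-d: at least 5 of 20 (Table 18). Model: exact binomial.

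**Step 1: confirm the model on the plan's other figures.**

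| Statement | Formula | Computed | Stated |
|---|---|---|---|
| Rules 1a-c met at 10% | 1 − 0.90^20 | 87.8% | 88% |
| Rules 2a-d not met at 16% | P(X ≤ 4; 20, 0.16) | 79.4% | 80% |
| Rules 2a-d met at 25% | P(X ≥ 5; 20, 0.25) | 58.5% | 60% |
| At least one AE at 7.8% (section 10.1.1) | 1 − 0.922^20 | 80.3% | 80% |
| At least one AE at 10.9% (section 10.1.1) | 1 − 0.891^20 | 90.1% | 90% |

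All agree to within 1.5 percentage points, so this is the model the protocol uses.

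**Step 2: apply it to the disputed clause.** P(not met) = (1 − p)^20.

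| True incidence p | P(not met) | P(met) |
|---|---|---|
| 0.5% | 0.995^20 = 90.5% | 9.5% |
| 0.75% | 0.9925^20 = 86.0% | 14.0% |
| 1% | 0.99^20 = 81.8% | 18.2% |

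The incidence at which P(not met) equals 90% is p = 1 − 0.9^(1/20) = 0.525%. The clause is false from there up to 1%, roughly the upper half of the range it covers. At the boundary it is about 8 points too high.

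**Step 3: look for a reading that gives the stated figure.**

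| Variant | P(not met) at 1% | P(met) at 10% |
|---|---|---|
| n = 20, trigger ≥ 1 (as written) | 81.8% | 87.8% |
| n = 18 | 83.5% | 85.0% |
| n = 36 | 69.6% | 97.8% |
| n = 40 (both groups) | 66.9% | 98.5% |
| n = 10 | 90.4% | 65.1% |
| n = 20, trigger ≥ 2 | 98.3% | 60.8% |

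A Poisson approximation with n = 20 gives 81.9% at 1%. More than 90% at 1% with a one-subject trigger needs 10 subjects or fewer (0.99^10 = 90.4%; 0.99^11 = 89.5%). No variant gives both more than 90% not met at 1% and about 88% met at 10%.

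**The case against.** The strongest point is that little follows from the error. The sentence only describes a curve. The operative rules are in Tables 17 and 18, a single event triggers a hold whatever its probability, and the hold is then reviewed before the sponsor decides how to proceed. Neither the sample size nor the SAP uses the figure. This stands, and it is why the point is minor.

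Figure 2 was not available for this check, so the plotted curve may be right and only its verbal summary wrong. That also stands: the finding is about the sentence. If the curve agrees with the sentence, both need correcting.

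The 18.2% is also not the trial's overall chance of a pause. It concerns one rule in one group of 20. Rules 1a-c are assessed by blinded investigators, and Table 17, unlike rules 2b-d in Table 18, does not confine them to the RSV group. There are three such rules, and an event after dosing is complete can pause nothing. The overall chance depends on placebo-group rates, overlap between rules and timing, none of which the documents give. This is correct, and it limits the conclusion to the quantity section 8.7.3 describes. It does not rescue the sentence: counting both groups at the same incidence lowers the figure further.

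Finally, reading the clause as meaning well below 1% does not work. The companion figures at 10%, 16% and 25% hold at their stated boundaries to within 1.5 points.

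**Conclusion.** The concern holds, as a minor arithmetic error. For one rule 1a-c in one group of 20, the chance of not being met at 1% incidence is 81.8%, so the chance of being met is 18.2% rather than under 10%. The stated 90% is true only below about 0.53%. This rests on a one-subject trigger, 20 subjects, and independent subjects with a common incidence, which is the model that fits the section's other figures. The error understates how readily a single-event rule is met at low incidence. It does not weaken subject protection.

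The gaps of 0.2 to 1.5 points in the other three boundary figures are consistent with rounding or reading from a curve and are not errors of substance.

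**What to change.** Restate the clause in section 8.7.3 in one of two ways: more than 81% chance of not being met for a true incidence below 1%, or more than 90% for a true incidence below 0.5%. Check Figure 2 against the corrected text.

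Optional tidying in the same edit:
- Give the other boundary figures as 87.8% met at 10%, 79.4% not met at 16% and 58.5% met at 25%.
- In Table 19 (section 10.1.1), correct the percentage labels for 17 and 18 of 20 subjects. They are shown as 90% and 95% and should be 85% and 90%. The counts and confidence limits in those rows are right.

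The cost is one text correction in the protocol. The holding rules, conduct, analysis and sample size stay as they are.

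### Section 8.7.3 overstates how rarely holding rules 1a-c would be met: at a true 1% rate the chance of not meeting a given rule in one group of 20 is 81.8%, not above 90%

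*Protocol*

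**What the plan says.** Section 8.7.3 introduces its probabilities with "Figure 2 gives the probability of not meeting each holding rule 1 and 2 for 20 subjects per group", and the caption of Figure 2 calls it a "risk assessment curve for 1 group based on the proposed safety holding rules". The first bullet below the figure gives two bounds for each of rules 1a-c. The first is "more than 90% chance of not being met for vaccination with a true incidence rate below 1"%. The second is a chance above 88% of being met when the true rate is above 10%. The second bullet gives two similar bounds for rules 2a-d.

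Table 17 lists rules 1a-c; rule 1a, for example, is "Death or any life-threatening SAE". For all three the required number of subjects is one or more. Section 8.7.2 says that "meeting any of these holding rules will trigger a hold of vaccination".

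**The concern.** With a one-subject trigger and 20 subjects, the chance of seeing no event falls quickly as the rate rises, and a 90% chance of no event does not fit a rate as high as 1%. Section 10.1.1 works with the same quantity at n = 20, so the protocol itself supplies the means to see the mismatch.

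The sentence is the protocol text's only numerical statement of how often rules 1a-c would be met at low event rates. Under Section 8.7 the internal safety review committee (iSRC) reviews the protocol. Once an investigator identifies that a rule is met, vaccination stops in every centre and the case goes to internal and iSRC review, after which "the Sponsor will decide to continue the conduct of, suspend or modify the study". A reader who relies on the sentence would expect a single-event hold less often than the design delivers.

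**Working it through.** **Inputs**

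- Subjects per group: n = 20 (Section 8.7.3).
- Scope: each rule separately, one group (Section 8.7.3 and the Figure 2 caption).
- Trigger for 1a, 1b and 1c: at least 1 subject (Table 17).
- Trigger for 2a-d: at least 5 of 20 (Table 18).

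**Model.** The number of subjects with an event is binomial with n = 20 and true rate p. For rules 1a-c, P(not met) = (1-p)^20 and P(met) = 1 - (1-p)^20.

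**Step 1: confirm the model on the plan's other figures**

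| Where | Stated | Recomputed |
|---|---|---|
| 8.7.3, rules 1a-c met at 10% | above 88% | 1 - 0.9^20 = 87.8% |
| 8.7.3, rules 2a-d not met at 16% | above 80% | P(X ≤ 4) = 79.4% |
| 8.7.3, rules 2a-d met at 25% | above 60% | P(X ≥ 5) = 58.5% |
| 10.1.1, at least one AE at 7.8% | 80% | 1 - 0.922^20 = 80.3% |
| 10.1.1, at least one AE at 10.9% | 90% | 1 - 0.891^20 = 90.1% |

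All five agree to within 1.5 percentage points.

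**Step 2: test the disputed figure**

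| True rate p | P(not met) = (1-p)^20 | P(met) |
|---|---|---|
| 0.5% | 90.5% | 9.5% |
| 0.6% | 88.7% | 11.3% |
| 0.75% | 86.0% | 14.0% |
| 0.9% | 83.5% | 16.5% |
| 1% | 81.8% | 18.2% |

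At 1% the gap from the stated 90% is 90 - 81.8 = 8.2 points.

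**Step 3: find where 90% holds.** Solving (1-p)^20 = 0.90 gives p = 1 - 0.9^(1/20) = 0.525%. The claim is true below that rate and false from there up to 1%, which is nearly the upper half of the range it covers.

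**Step 4: look for a setting that rescues both halves of the bullet**

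| Setting | Not met at 1% | Met at 10% |
|---|---|---|
| n = 20, trigger 1 (as written) | 81.8% | 87.8% |
| n = 18, trigger 1 (10% non-evaluable) | 83.5% | 85.0% |
| n = 36, trigger 1 (evaluable, both groups) | 69.6% | 97.7% |
| n = 40, trigger 1 (both groups) | 66.9% | 98.5% |
| n = 10, trigger 1 | 90.4% | 65.1% |
| n = 20, trigger 2 | 98.3% | 60.8% |

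With a one-subject trigger, 0.99^n exceeds 90% only for n of 10 or less (0.99^10 = 90.4%, 0.99^11 = 89.5%). At those sizes 1 - 0.9^n is at most 65.1%. No group size with the Table 17 trigger therefore gives both the 90% and the 88%.

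**The case against.** The arithmetic is not in dispute, and no reading of the documents rescues the sentence. The case on the other side concerns weight and precision.

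- **No decision depends on the figure.** Rules 1a-c act on one subject whatever the probability, and the investigator assesses them continuously. That the iSRC reads the protocol does not show that anyone uses the 90%. This stands, and it keeps the point minor.
- **The text says below 1%, not at 1%.** This is correct: 81.8% is the limit at the edge of the range. But the claim already fails inside the range, for example at 0.6% (88.7%) and 0.9% (83.5%).
- **Rules 1a-c are not more sensitive than stated at every rate.** This also stands. The understatement of sensitivity applies at low true rates only. At the other bounds the small gaps run the opposite way: 87.8% against 88% for rules 1a-c, and 58.5% against 60% for rules 2a-d. The latter is a coarse rounding, though far smaller than 8.2 points.
- **A protocol change is not free.** The SAP records the protocol as final on 30 April 2019, and Section 12.4.1 requires ethics approval of amendments. This bears on when to correct the sentence, not on whether it is wrong.
- **Figure 2 may be right.** It could not be seen, so the finding covers the sentence only.

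**Conclusion.** The concern holds. For one rule in one group of 20, the chance of not meeting the rule falls to 81.8% at a true rate of 1%, so the chance of meeting it rises to 18.2% where the text implies under 10%. The stated bound is wrong for true rates from about 0.53% to 1%.

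This rests on independent subjects with a common event rate, all 20 observed, and the Table 17 trigger. The protocol's other probabilities follow the same model. The 18.2% is per rule and per group. It is not the study-level chance of a hold, which the documents do not give.

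The error is confined to a description of operating characteristics. At low rates, rules 1a-c would be met more often than the text says, so subjects face no added risk. The holding rules, sample size and analyses are unaffected.

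**What to change.** Leave the rules as they are and correct the first bullet of Section 8.7.3 in one of two ways. Either keep the 90% and lower the rate to 0.5% (exact value there 90.5%), or keep the 1% and lower the probability to more than 81% (exact value there 81.8%). The documents do not show which was intended, and both are true.

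Check that the rule 1 curve in Figure 2 passes through 81.8% at 1%. Optionally, restate the second bullet as about 79% not met at 16% and about 59% met at 25%.

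The cost is one number and a look at the figure. A stand-alone amendment would be out of proportion; the correction can go into the next amendment made for another reason, or be noted in the study report.
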